SGPT	Serum Glutamic Pyruvic Transaminase
ST2	Suppressor of tumorigenicity-2
TCI	The Tisch Cancer Institute at Mount Sinai
TNFR1	Tumor necrosis factor receptor-1
UGI	Upper Gastrointestinal
VZV	Varicella-Zoster Virus

STUDY SYNOPSIS

Title	Itacitinib Monotherapy For Low Risk Graft-Vs-Host Disease				
Phase	11				
Methodology	Open label, single arm, non-inferiority study				
Study Duration	2 years				
Study Center(s)	Mount Sinai (lead), City of Hope, Emory University, Massachusetts General, Mayo Clinic, Ohio State University, University of Kansas, University of Pennsylvania, Vanderbilt University, Children's Hospital of Los Angeles, Children's Hospital of Philadelphia, MD Anderson Cancer Center, Fred Hutchinson Cancer Research Center				
Objectives	 Primary Objective: To determine the effectiveness of itacitinib monotherapy as primary treatment of newly diagnosed, low-risk acute graft-versus-host disease (GVHD) defined by standard risk clinical criteria (Minnesota) and low risk biomarkers (Ann Arbor 1). Secondary Objectives: To assess the safety of itacitinib monotherapy as the primary treatment of newly diagnosed, low-risk acute GVHD defined by standard risk clinical criteria (Minnesota) and biomarkers (Ann Arbor 1). Secondary Objectives: To assess the safety of itacitinib monotherapy as the primary treatment of newly diagnosed, low-risk acute GVHD defined by standard risk clinical criteria (Minnesota) and biomarkers (Ann Arbor 1 GVHD) To determine the incidence of serious infectious complications in patients with GVHD treated with itacitinib To determine the GVHD response rate to systemic steroid 				
Number of Subjects	70				
Inclusion Criteria	 Newly diagnosed GVHD that meets criteria for Minnesota standard risk Ann Arbor 1 GVHD by biomarkers GVHD not previously treated systemically (topical therapies and non-absorbed steroids are allowed) Any donor type, HLA-match, conditioning regimen is acceptable Age 12 years and up (children <18 years must also weigh 50 kg or more) Patients must be engrafted post-transplant (ANC ≥500/µL and platelet count ≥20,000). Use of growth factor supplementation to maintain neutrophil count is allowed. Direct bilirubin must be <2 mg/dL unless the elevation is known to be due to Gilbert syndrome within 3 days prior to enrollment. ALT/SGPT and AST/SGOT must be <5x the upper limit of the normal range within 3 days prior to enrollment. Signed and dated written informed consent obtained from patient or legal representative. 				

Exclusion Criteria	 Patients currently being treated with any JAK inhibitor including ruxolitinib Relapsed, progressing, or persistent malignancy requiring withdrawal of systemic immune suppression Patients with uncontrolled infection (i.e., progressive symptoms related to infection despite treatment or persistently positive microbiological cultures despite treatment or any other evidence of severe sepsis) Severe organ dysfunction including requirement for dialysis, mechanical ventilation or oxygen supplementation exceeding 40% FiO2 within 7 days of enrollment. Creatinine clearance or estimated glomerular filtration rate <30 ml/min as calculated by institutional practice (e.g., Cockcroft- Gault equation, CKD-EPI equation, etc) A clinical presentation resembling de novo chronic GVHD or overlap syndrome developing before or present at the time of enrollment Patients receiving corticosteroids >10 mg/day prednisone (or other steroid equivalent) for any indication within 7 days before the onset of acute GVHD except for adrenal insufficiency or premedication for transfusions/IV meds Patients who are pregnant Patients receiving investigational agents within 30 days of enrollment. However, the Principal Investigator (PI) may approve
	to interfere with the safety or the efficacy of itactinib 10. History of allergic reaction to itacitinib or any JAK inhibitor
Study Product(s), Dose, Route, Regimen	Itacitinib 200 mg orally daily for 28 day induction cycle followed by 28 day maintenance cycle
Duration of Administration	56 days
Statistical Methodology	The primary study measure is the proportion of patients who achieve CR or PR by day 28 of treatment with itacitinib without the addition of any other systemic GVHD treatment including steroids. The expected proportion of low-risk acute GVHD patients who achieve CR or PR by day 28 of standard steroid treatment is 67%. Extensive preliminary discussion indicate that physicians would accept a 15% decrease in the overall response rate to primary GVHD treatment (from 67% to 52%) if steroid treatment could be avoided in the responders without an increase in the incidence of steroid refractory GVHD. A sample size of 70 achieves 81% power to detect a non-inferiority proportion of 52% using a one-sided exact test with a significance level of 0.04 calculated using binomial enumeration of all possible outcomes. This study will terminate early if the incidence of steroid refractory GVHD exceeds the historical rate of 38% or if the incidence of non-relapse mortality (as a measure of all potential toxicities) exceeds the historical rate of 9% (section 8.7).

1.0 BACKGROUND AND RATIONALE

1.1 Acute GVHD

Hematopoietic cellular transplantation (HCT) is an important treatment for high-risk hematologic malignancies whose curative potential depends on the graft-versus-leukemia (GVL) effect which is mediated by alloreactive T cells in the donor graft. GVL effects are closely associated with graft-versus-host disease (GVHD), which is mediated by those same T cells¹. Graft-versus-host disease (GVHD) targets the skin, liver and GI tract. GVHD is the major cause of non-relapse mortality (NRM) after HCT¹⁻³. Maximal GVHD grade, which only reflects response to treatment, correlates with NRM⁴. GVHD symptom severity at presentation modestly correlates with outcomes but not sufficiently to guide treatment^{5,6}. For example, the Minnesota classification system uses GVHD symptom severity at diagnosis to stratify patients into standard and high risk groups with significantly different risk for NRM (22% vs 43%, p<0.001)⁶. The risk for NRM even in the favorable group remains too high to de-escalate treatment, high dose systemic glucocorticoids (steroids). As a result, primary treatment for GVHD has not changed over the past 40 years⁷.

1.2 Steroid Treatment

Systemic steroid treatment is well known to increase the risk of serious infections such as bacterial sepsis and bacteremia⁸⁻¹¹, viral disease such as CMV¹¹⁻¹⁴ and EBV^{11,15}, and invasive fungal infections^{10,11}. These complications have remained morbidities in the HCT literature despite modern infection prophylaxis^{8,10,11,16-19}.

HCT patients are highly immunocompromised, both as a result of the pre-transplant conditioning regimen and GVHD prophylaxis. GVHD itself is immunosuppressive^{16,17}. To better understand the contribution of steroid treatment to the infectious complication rate in current patients, we analyzed the six-month incidence of serious infections in 79 patients from two centers (Icahn School of Medicine at Mount Sinai and Ohio State University) transplanted between 2014-2017 [Fig 1]. Patients were categorized into two groups – those who were diagnosed with GVHD that was treated with systemic steroid therapy (n=43) and those who did not develop GVHD and did not receive

systemic steroid therapy (n=36). We analyzed rates of blood culture proven bacterial infections, viral reactivations requiring treatment (CMV and EBV). and proven invasive fungal infections. Patients who developed more than one infection in a category (e.g., episodes multiple of bacterial sepsis) were counted only once. As expected, systemic steroidtreated GVHD patients developed significantly more bacterial (37% vs 12%, p=0.009) and viral infections (CMV 54% vs

28%, p=0.02; EBV 12% vs 0%, p=0.04). Interestingly, the incidence of invasive fungal infections was lower than published reports and not statistically different between the two groups, perhaps a result of the widespread adoption of highly effective broad spectrum anti-fungal prophylaxis^{10,11,18,19}. The proportion of patients developing at least one of these life threatening bacterial, viral, or fungal infections was significantly higher in the steroid exposed group (59% vs 33%, p=0.03).

It is important to note that children are susceptible to the same steroid related toxicities as adults as well as additional toxicities. Corticosteroids are potent inhibitors of linear growth, especially during the adolescent growth spurt²⁰. Likewise, the incidence of corticosteroid-related osteonecrosis, a debilitating skeletal complication, is highest in adolescents, presumably reflective of the vulnerability of rapidly growing bone²¹. Steroid-sparing GVHD treatments are thus even more urgently needed in the high risk adolescent population.

1.3 GVHD Biomarker Algorithms Risk Categorize Patients

The past several years have shown remarkable advances in the prediction of long term outcomes by biomarkers²²⁻²⁶. The best algorithm requires only measurements of ST2 and REG3 α at GVHD diagnosis to accurately stratify patients into three distinct "Ann Arbor" risk groups (Fig 2)²⁷. ST2 and REG3 α are closely associated with GI GVHD^{22,28} and increased concentrations at GVHD diagnosis, (i.e. Ann Arbor 3) predict for the development of steroid-refractory GI GVHD while low concentrations (i.e., Ann Arbor 1) predict for steroid responsiveness and low rates of NRM.

As noted above, clinical symptom severity at GVHD onset as determined by Minnesota risk, correlates with outcomes⁶. Patients with Minnesota standard risk GVHD, the more favorable group, primarily present with skin GVHD or mild GI GVHD. We hypothesized that the biomarker algorithm would identify a low risk subset within this population (Fig 3). We studied 183 patients with newly diagnosed GVHD from the Mount Sinai Acute GVHD International Consortium (MAGIC). Patients with both favorable clinical and biomarker features (i.e., Minnesota standard risk and Ann Arbor 1) had significantly lower rates of six-month NRM compared to patients with Minnesota standard risk but Ann Arbor 2/3 GVHD (9% vs 25%, p=0.002). This novel low risk population comprised 51% (94/183) of the standard risk patients, had high response rates to systemic steroid therapy (67% CR/PR), and represents the ideal population in which to test steroid-free approaches to GVHD treatment.

1.4 JAK-inhibition as a target for GVHD

The JAK-STAT pathway provides promising targets for GVHD treatment with less potential toxicity than systemic corticosteroids.

GVHD pathogenesis is a three step process consisting of damage to a transplant recipient's tissue during conditioning which primes antigen presenting cells such as dendritic cells, consequent donor T-cell activation, and subsequent T-cell mediated tissue damage to the host¹. The JAK-STAT pathway, whose purpose is to regulate gene expression via cytokine binding to homodimers or heterodimers of JAK1, JAK2, JAK3 and/or TYK2²⁹, has been implicated in all three phases of

GVHD development³⁰. Preclinical and clinical data from studies with ruxolitinib, a JAK1/2 inhibitor, provide a strong rationale to further investigate JAK inhibitors in patients with GVHD. In vivo JAK/STAT-signaling inhibition improved survival of mice with GVHD, and decreased dendritic cell maturation, T cell activation, and chemokine-induced T cell migration to the target tissues, liver and small intestine³¹. Biochemical studies of these mice showed decreased TNF α and IL12p70 supporting the role of JAK1/JAK2 signaling in T cell activation and trafficking. Additionally, ruxolitinib treatment of murine GVHD increased FoxP3+ regulatory T cells, which are important regulators of GVHD^{31,32}.

Ruxolitinib is associated with clinical benefit in human disease³⁰. Zeisser et al reported that the overall response rate (ORR) for patients with steroid-refractory GVHD treated with ruxolitinib was 81.5% (44/54)³³. A similar high ORR (85.4%, 35/41) was observed in patients with steroid refractory chronic GVHD³³. In a small pediatric study of 11 children ages 1 to 16 years with GVHD refractory to multiple lines of treatment, including steroids, the ORR was 45% (5/11)³⁴. The primary complication of ruxolitinib treatment was grade 3-4 cytopenias which developed in 18% of patients. High rates of ruxolitinib-related grade 3-4 cytopenias have also been identified in patients treated with myelofibrosis, a JAK/STAT dependent myeloproliferative disorder³⁵⁻³⁷. These effects are likely mediated by JAK2 inhibition, as homodimers of JAK2 are associated with G-CSF, GM-CSF, EPO, and TPO signaling²⁹. These undesirable hematologic side effects of ruxolitinib led to the development of a more selective JAK1 inhibitor.

Itacitinib, a selective JAK1 inhibitor

Itacitinib (INCB39110) is an oral selective JAK1 inhibitor that potently inhibits JAK1 (half maximal inhibitory concentration, IC_{50} = 3.6 nM at 1 mM adenosine triphosphate concentration), with 22- to >500-fold selectivity over the other JAK family members, JAK2, JAK3, and TYK2. It does not significantly inhibit (< 30% inhibition) a broad panel of approximately 60 other kinases. Itacitinib potently inhibits the phosphorylation of STAT proteins and the production of proinflammatory factors induced by other cytokines, such as IL-23 and IL-6 with IC_{50} values of approximately 30 nM to 100 nM. In contrast, itacitinib shows less inhibition in cell-based assays dependent on JAK2 with IC_{50} values of approximately 1 μ M or greater, suggesting that itacitinib is JAK2 sparing in cells. In *in vivo* models of JAK dependent malignancy, itacitinib impedes subcutaneous tumor growth of INA-6 cells expressing WT JAKs when administered by continuous infusion, achieving plasma concentrations well below those necessary to inhibit JAK2.

In ongoing and completed clinical pharmacology studies, itacitinib was generally safe and welltolerated in 284 healthy subjects, with few discontinuations. The majority of treatment-emergent adverse events (TEAEs) were mild in severity. There have been no clinically significant, unanticipated safety findings or trends observed. The main drug effect identified was a rapidly reversible dose-related decrease in neutrophil counts presumably caused by neutrophil margination; neutrophil decreases generally resolved within 24 to 48 hours of dose discontinuation. Other reversible hematologic abnormalities, including decreased reticulocyte count, were observed after multiple-dose administration of higher dose levels at which JAK2 inhibition was noted (*Itacinib investigator brochure v9, Feb 9 2017*). In contrast to ruxolitinib, withdrawal syndrome has not been observed with itacitinib.

Itacitinib has demonstrated an encouraging safety profile in clinical trials for myelofibrosis and psoriasis. Mascarenhas et al. reported that itacitinib, administered at 100 mg BID, 200 mg BID, or 600 mg daily decreased the symptom burden of myelofibrosis patients³⁸. At the highest dose levels, only one patient (3.1%) experienced grade 4 thrombocytopenia, no patient experienced grade 3-4 neutropenia, and 25% patients developed grade 3 anemia. The rate of grade 3-4 neutropenia, and thrombocytopenia *decreased* with *increased* itacitinib dose, suggesting that cytopenias were a consequence of the myelofibrosis rather than the drug. Likewise, no significant hematologic toxicity was noted in a phase II trial of itacitinib for psoriasis³⁹. Non-hematologic toxicities were generally grade 1-2.

In total, 777 subjects have been exposed to itacitinib across all clinical trials. Serious adverse effects have been infrequent. Expected serious adverse events include anemia (2.4%), fever (1%), and urinary tract infection (1%). When all clinical experiences are taken together itacitinib has a favorable safety profile.

Itacitinib for the treatment of acute GVHD

Thirty-one subjects have received itacitinib in combination with high dose steroids for the treatment of moderate to severe acute GVHD in a randomized, phase I trial. Patients had either newly diagnosed (n=17) or steroid-refractory (n=14) GVHD when randomized to either 200 mg daily or 300 mg daily of itacitinib. The overall response rate as a first line therapy for GVHD was 83.3% and 64.7% in the steroid refractory cohort⁴⁰. The most common adverse events were thrombocytopenia (26.7%), diarrhea (23.3%), peripheral edema (20%), fatigue (16.7%) and hyperglycemia (16.7%), all of which are more likely related to the underlying GVHD and/or concurrent use of high dose steroids than to itacitinib because these events were not observed in other itacitinib trials. The incidence of infections was not higher than expected. There were three CMV infections and three cases of sepsis out of 31 patients. GI bleeding, a symptom of severe GI tract GVHD, was observed in three patients. These preliminary data demonstrate both a promising efficacy signal and a good safety profile for itacitinib for the treatment of acute GVHD.

Itacitinib dosing

In the phase I aGVHD trial, the pharmacokinetics of itacitinib were evaluated using plasma samples collected pre-dose and on days 1 and 7 at 1 hour, 2 hours, and 4 to 8 hours post-dose. Although inter-subject variability was found to be high, PK exposure (C_{max} and AUC) was consistent with historical data, and a large overlap in steady-state exposure was observed between the 200 mg and 300 mg cohorts. Given the similarities in PK and efficacy between dose groups, and the increased likelihood of unwanted JAK2 inhibition at higher doses, itacitinib at 200 mg daily has been identified as the recommended dose for future GVHD studies.

1.5 Mount Sinai Acute GVHD International Consortium (MAGIC)

MAGIC, a collaboration of 23 international HCT centers in the United States, Canada, Germany, Italy, and Thailand, was formed in 2013 for the purposes of conducting innovative translational clinical trials in GVHD. Because GVHD grading can be inconsistent among centers⁴¹, MAGIC centers follow standardized GVHD staging and grading guidance⁴² whose use is reinforced by monthly webinars and remote data audits conducted by the MAGIC Data Coordinating Center (DCC) in New York. All MAGIC centers participate in an observational trial of prospective data and research sample collection and as a result collection of research samples at GVHD diagnosis is very high (85%). MAGIC centers in the US are already highly experienced in enrolling patients on GVHD biomarker guided treatment trials. For example, US centers have submitted screening samples from more than 300 patients to the CLIA-certified Mount Sinai GVHD laboratory for real time Ann Arbor scoring since 2016. Conduct of this low risk GVHD trial through MAGIC will leverage an existing infrastructure with substantial experience in successful conduct of similar trials.

1.6 Correlative Studies

Serial serum biomarkers. GVHD biomarkers are prognostic early after HCT, at diagnosis, and during treatment^{23,26,27}, but the relationship between changes in GVHD biomarker concentrations measured serially over time and outcomes is not yet well understood. We will collect four weekly samples from patients on this study and correlate changes in biomarkers with long term outcomes. We expect that GVHD biomarkers will remain low in study patients who respond to itacitinib treatment, but will rise in non-responders.

1.7 Summary of Study Rationale

Standard treatment for GVHD involves high doses of steroids which are highly toxic. The MAGIC algorithm identifies the low risk patients most likely to benefit from a steroid-free GVHD treatment approach. Itacitinib at a 200 mg/day dose has been shown to be safe with few side effects and

phase I data in patients with GVHD showed encouraging efficacy. In this study, patients with low risk GVHD will receive itacitinib monotherapy as first line treatment. Patients will be carefully monitored for efficacy and toxicity and the salvage rate with steroids for patients who do not respond to primary therapy with itacitinib will also be closely monitored. The use of objective laboratory measures in addition to clinical symptoms has the potential to transform GVHD therapy and represents a key step towards a precision medicine approach for GVHD. This phase II study will develop the data required for a definitive randomized phase III trial comparing itacitinib to steroid treatment for low risk GVHD.

2.0 STUDY OBJECTIVES

2.1 Primary Objectives

2.1.1 To determine the effectiveness of itacitinib monotherapy as primary treatment of newly diagnosed, low-risk acute GVHD defined by standard risk clinical criteria (Minnesota) and low risk biomarkers (Ann Arbor 1).

2.2 Secondary Objectives

- 2.2.1 To assess the safety of itacitinib monotherapy in these patients.
- 2.2.2 To determine the incidence of serious infectious complications in patients with GVHD treated with itacitinib
- 2.2.3 To determine the incidence of steroid refractory GVHD in patients whose GVHD is not responsive to itacitinib

2.3 Primary Endpoint

Proportion of patients who achieve CR or PR by day 28 of treatment with itacitinib without the addition of any other systemic GVHD treatment including steroids.

CR is defined as absence of GVHD symptoms. PR is defined as improvement in one or more organs involved with GVHD symptoms without progression in other organs. For a response to be scored as CR or PR on day 28, the patient must be in CR or PR on day 28 and have had no intervening systemic therapy for acute GVHD other than itacitinib.

Secondary endpoints:

- Cumulative incidence of steroid-refractory GVHD (defined as GVHD that worsens (increase by one or more grade) after 3 days, or fails to respond to treatment within 7 days (for GVHD grade III) or 14 days (for GVHD grade II) or 2nd line therapy beyond systemic steroid treatment is begun within 28 days of starting steroids.
- 2. Distribution of maximal GVHD grade (I-IV) by day 28 after starting treatment with itacitinib
- 3. Cumulative incidence of serious infections (defined as bacteremia, CMV infection needing treatment, EBV infection needing treatment, or invasive fungal infection)
- 4. Overall survival at 6 and 12 months
- 5. Cumulative incidence of NRM at 6 and 12 months
- 6. Relapse rate at 6 and 12 months
- 7. Cumulative incidence of chronic GVHD requiring systemic steroid treatment by one year from enrollment

8. Cumulative steroid dose (over 4 weeks) in patients who receive steroids as second line therapy

Safety endpoints

1. Number and proportion of patients developing reportable AEs and SAEs according to relatedness to study drug and stratified by severity

Exploratory endpoints

1. GVHD biomarker concentrations (ST2 and REG3) and their associations with clinical endpoints at day 28 after starting treatment with itacitinib

The two hypotheses are: 1) that GVHD biomarkers will remain low in study patients who respond to itacitinib treatment, but will rise in non-responders and (2) biomarker concentrations will be equivalent to those in historical control patients who respond to steroid treatment for low risk GVHD.

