3.1 Inclusion Criteria

- 3.1.1 Newly diagnosed GVHD that meets criteria for Minnesota standard risk (see section 7.0)
- 3.1.2 Ann Arbor 1 GVHD by biomarkers
- 3.1.3 GVHD not previously treated systemically (topical therapies and non-absorbed steroids are allowed)
- 3.1.4 Any donor type, HLA-match, conditioning regimen is acceptable
- 3.1.5 Age 12 years and up (children <18 years must weight 50 kg or more)
- 3.1.6 Patients must be engrafted post-transplant (ANC ≥500/µL and platelet count ≥20,000). Use of growth factor supplementation to maintain neutrophil count is allowed.
- 3.1.7 Direct bilirubin must be <2 mg/dL unless the elevation is known to be due to Gilbert syndrome within 3 days prior to enrollment.
- 3.1.8 ALT/SGPT and AST/SGOT must be <5x the upper limit of the normal range within 3 days prior to enrollment.
- 3.1.9 Signed and dated written informed consent obtained from patient or legal representative.

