7.0 GVHD CLINICAL STAGING

GVHD clinical staging will be according to the established criteria used for MAGIC clinical trials.

	Stage 0	Stage 1	Stage 2	Stage 3	Stage 4
Skin	No rash	Rash < 25% BSA	25-50%	> 50% Generalized erythroderma	Plus bullae and desquamation >5% BSA
Liver	Bilirubin ≤ 2 mg/dl	2.1-3 mg/dl	3.1-6mg/dl	6.1-15mg/dl	>15mg/dl
GI tract	Adult: < 500 ml/day Children <10 mg/kg/d	Adult: 500–1000 ml/day Children 10-19.9 mg/kg/d	Adult: 1001-1500 ml/day Children 20- 30 mg/kg/d	Adult: >1500 ml/day Children > 30 mg/kg/d	Severe abdominal pain +/- ileus, frank blood or melena (regardless of stool volume)
UGI		Severe nausea/vomiting			

• For GI GVHD, children is defined as <18 years of age and <50 kg weight

• For stage 4 GI GVHD, severe abdominal pain is defined as (1) pain that requires opioid use **and** (2) pain that significantly impacts on performance status as determined by the treating physician

• Comprehensive GVHD staging guidance is provided in the MAGIC GVHD Staging Guidance.

Overall Clinical Grade:

Grade 0	No stage 1-4 of any organ
Grade I	Stage 1-2 skin and no liver or GI involvement
Grade II	Stage 3 skin and/or Stage 1 liver and/or Stage 1 GI
Grade III	Stage 0-3 skin with Stage 2-3 liver and/or Stage 2-3 GI
Grade IV	Stage 4 in any target organ (skin, liver, GI)

Minnesota Risk Scoring⁶:

Standard Risk:

Stage 1-3 skin (single organ system)
Stage 1-2 GI (single organ system)
Stage 1-3 skin + Stage 1 GI (two organ system involvement)
Stage 1-3 skin + Stage 1-4 liver (two organ system involvement)
High Risk: Any other combination of single or dual organ aGVHD stages

Minnesota risk scoring calculator: http://z.umn.edu/MNAcuteGVHDRiskScore

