11.3 Data Analysis Plans

The primary endpoint is the proportion of patients who achieve CR or PR by day 28 of treatment with itacitinib without the addition of any other systemic GVHD treatment including steroids. Death, lack of GVHD response to itacitinib by day 28 of treatment, or initiation of steroid or other systemic immunosuppressive therapy for GVHD will be considered failures for this endpoint. The proportion of patients who achieve CR or PR by day 28 in the study patients will be compared to the historical control rate of 67%.

Secondary outcomes such as cumulative incidence of steroid-refractory GVHD, proportion of patients with maximal grade I, II, III, and IV GVHD by day 28 after starting treatment with itacitinib, cumulative incidence of serious infections, cumulative incidence of hematologic toxicities, cumulative steroid dose over four weeks in patients who fail itacitinib monotherapy, overall survival at 6 and 12 months, cumulative incidence of NRM at 6 and 12 months, relapse rate at 6 and 12 months, and cumulative incidence of chronic GVHD requiring systemic steroid treatment by one year will be estimated and compared to historical controls.

Continuous variables will be summarized using standard summary statistics such as number of observations (n), mean, standard deviation (SD), minimum and maximum values, median, and 1st and 3rd quartiles. Categorical variables will be summarized in frequency tables as counts and percentages.

Cumulative incidence of non-relapse mortality will be estimated by Gray's method⁵³ and relapse will be considered as a competing risk. Disease free and overall survival, defined as the time from the transplantation to death or to last follow-up if alive, will be estimated by the method of Kaplan-Meier and the probability curves and 95% confidence intervals will be provided based on the method of Brookmeyer and Crowley⁵⁴.

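### Maximal GVHD grade by day 28 takes no account of entry grade, so its comparison with historical controls mixes case mix at entry with worsening on treatment

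*Combined protocol and SAP*

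**What the plan says.** Section 2.3 lists as its second secondary endpoint "Distribution of maximal GVHD grade (I-IV) by day 28 after starting treatment with itacitinib". Section 11.1 repeats it in similar terms, and section 11.3 has "proportion of patients with maximal grade I, II, III, and IV GVHD by day 28 after starting treatment with itacitinib" among the outcomes that "will be estimated and compared to historical controls". None of these places mentions the grade at entry, and the scale has no grade 0.

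Entry requires "Newly diagnosed GVHD that meets criteria for Minnesota standard risk (see section 7.0"). The standard-risk list in section 7.0 includes "Stage 1-3 skin (single organ system") and "Stage 1-2 GI (single organ system"). The same section defines grade I as skin stage 1-2 alone and grade III as "Stage 0-3 skin with Stage 2-3 liver and/or Stage 2-3 GI".

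The background in section 1.1 reads maximal grade as a measure of treatment effect: "Maximal GVHD grade, which only reflects response to treatment, correlates with NRM".

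A baseline rule exists for complete and partial response, which section 7.1.2 scores against staging on the day itacitinib began. There is none for maximal grade. Staging is scheduled on study days 0, 7, 14, 21 and 28 (section 6.2, time and events table).

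**The concern.** Every patient has GVHD on day 0, so a maximum that includes day 0 starts from the entry grade and can only stay there or rise. A grade III entrant who clears completely and a grade I entrant who worsens to grade III receive the same value. The section 1.1 premise, that maximal grade reflects only response to treatment, then fails for this endpoint: part of what it reports is the severity of the patients enrolled.

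This matters most for the planned comparison. Section 11.1 describes the historical controls as consortium patients with Minnesota standard-risk, Ann Arbor 1 GVHD. The trial also requires direct bilirubin below 2 mg/dL, with an exception for Gilbert syndrome (section 3.1.7), and section 11.1 states no such limit for the controls. The standard-risk list admits skin disease with liver stage 1-4, which maps to grades II to IV. If the controls include more liver involvement, trial patients could show lower maximal grades without any effect of the drug.

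**Working it through.** There is no planned figure to reproduce; the point is one of definition. It was checked in three steps.

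**1. Can entry grade vary?** The standard-risk list in section 7.0 gives 3 skin-only, 2 GI-only, 3 skin-plus-GI and 12 skin-plus-liver stage combinations, 20 in all. Mapped to the overall grade in the same section:

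| Combinations | Grade I | Grade II | Grade III | Grade IV |
|---|---|---|---|---|
| All 20 | 2 | 8 | 7 | 3 |
| The 8 without liver | 2 | 5 | 1 | 0 |

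The single grade III combination without liver is GI stage 2 alone. So even if the bilirubin limit removed all liver involvement, grades I, II and III would remain eligible. These are counts of combinations, not of patients.

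**2. What does the maximum return?** Grades on days 0, 7, 14, 21 and 28 for three example courses:

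| Course | Maximum with day 0 | Maximum after day 0 |
|---|---|---|
| III, II, 0, 0, 0 | III | II |
| I, I, II, III, III | III | III |
| III, 0, 0, 0, 0 | III | 0 (not on the scale) |

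With day 0 counted, the first two patients cannot be told apart. If 10%, 20% or 30% of the 70 patients entered at grade III (7, 14 or 21 patients) and all 70 reached complete response without first worsening, the table would still report 10%, 20% or 30% with maximal grade III-IV.

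**3. How large a gap can arise with no drug effect?** The documents give neither entry mixes nor a worsening rate, so all inputs here are assumptions. Suppose entry is at grades I to III only, and each patient rises by at most one grade, with probability w in both groups. Then

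P(maximal grade III-IV) = share entering at III + w × share entering at II.

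With w = 0.20:

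| Assumed entry mix I/II/III (%) | Calculation | Maximal III-IV |
|---|---|---|
| Trial 25/60/15 | 0.15 + 0.60 × 0.20 | 27% |
| Controls 10/60/30 | 0.30 + 0.60 × 0.20 | 42% |
| Trial 20/60/20 | 0.20 + 0.60 × 0.20 | 32% |
| Controls 15/60/25 | 0.25 + 0.60 × 0.20 | 37% |

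The gaps are 42 − 27 = 15 points and 37 − 32 = 5 points. Because the grade II shares are equal within each pair, the gap is simply the difference in the share entering at grade III. If two-grade rises also occurred with probability v among grade I entrants, the gaps would narrow by (0.25 − 0.10)v and (0.20 − 0.15)v.

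**The case against.** The case for leaving the plan alone has five parts.

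- **The floor is inferred.** No section says that day 0 counts. This is correct. Still, the wording sets only an upper time limit, and a I-IV scale accommodates every patient only if entry grade counts. If only later visits are meant, a grade 0 category is needed, and a grade III entrant who is still grade III on day 7 before clearing would still score III.

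- **Progression is caught elsewhere.** A reader might infer that the trial cannot show whether GVHD progresses without steroids. The documents do not support that. Partial response requires no worsening in other organs, response is scored against day 0 (sections 7.1.1 and 7.1.2), starting steroids counts as failure (section 11.3), and steroid-refractory GVHD has its own stopping boundary (section 8.7). The endpoint itself also moves: with an entry mix of 20/60/20, halving worsening from 30% to 15% takes maximal III-IV from 0.20 + 0.60 × 0.30 = 38% to 0.20 + 0.60 × 0.15 = 29%. What remains is that the primary endpoint pools worsening with stable disease, so no planned measure reports worsening on itacitinib separately.

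- **The dilution is partly an artefact.** The 9-point change above comes from collapsing to III-IV. The plan reports four categories. Under the same assumptions these go from 14/48/32/6% to 17/54/26/3%. The falls at grade II or higher, III or higher, and IV are 3, 9 and 3 points, which sum to the full 15-point change in worsening. Loss of sensitivity is therefore not a main ground here.

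- **The wide mixes may be unrealistic.** Controls come from the same clinical and biomarker stratum, the consortium uses standardised staging (section 1.5), and section 1.3 says standard-risk patients mostly present with skin or mild GI disease. That fits poorly with 30% entering at grade III and makes the lower end of the range more plausible. It does not show that the mixes are equal.

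- **No decision rests on it.** Section 11.2 bases the phase III decision on response rate, steroid-refractory GVHD, NRM and serious infections, and the stopping rules do not use maximal grade. This stands and limits the weight of the point.

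**Conclusion.** The concern holds in limited form. Maximal grade by day 28 is defined without reference to day-0 grade in a population that can enter at grade I, II or III, and section 11.3 plans a comparison with controls that does not account for entry grade. The comparison is therefore open to confounding by entry severity, and the bilirubin limit gives a reason in the documents why the mixes might differ.

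The 5 to 15 points are an illustration under assumed entry mixes and equal worsening, not an estimate for this trial. They also rest on day 0 being counted. The documents do not establish that the distribution mainly reproduces who was enrolled, since they give no entry mix.

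The consequence is a secondary comparison that could mislead. The primary result and the decision to proceed to phase III are not affected.

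**What to change.** In section 2.3 (secondary endpoint 2), section 11.1 and section 11.3:

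1. Keep the maximal-grade distribution as a description, and state whether the day-0 assessment counts. If it does not, add a grade 0 category.
2. Add a cross-table of day-0 grade by maximal grade through day 28.
3. Report the proportion of patients whose overall grade rises above the day-0 grade by day 28.
4. Make the historical-control comparison within day-0 grade, or standardise the controls to the trial's day-0 mix, applying the same counting rule to both groups.

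For trial patients this is a wording change and one table, because the staging is already scheduled. For controls, it should be confirmed that grade at start of treatment is available. The drawback is small strata: if 15% enter at grade III, that is 0.15 × 70 = 10.5, about 10 patients, and each one moves that stratum's proportion by about 10 points. Within-grade estimates will be imprecise and should be presented as such; standardisation gives a single summary but does not remove the imprecision.
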